8.8 Safety Evaluation

8.8.1 Extent of Exposure

The extent of exposure to study drug in each treatment group will be summarized by total number of days of exposure, total number of applications, number of missed applications and number and percentage of subjects who are compliant. A subject will be considered compliant with the dosing regimen if the subject applied 80% to 120% of the expected number of applications and did not miss more than 5 consecutive applications while enrolled in the study.

Days of exposure = Date of last study application – Date of first study application + 1

The total number of applications taken is as follows:

(Date of Last Application – Date of First Application + 1) – (Number of Days marked as missed applications on the CRF) + (Number of extra applications marked on the CRF)

If a subject did apply medication on the last day, the total number of applications expected is as follows:

Date Subject End Participation – Date of Baseline +1.

If the total number of applications exceeds 89 then it will be set to 89.

If a subject did not apply medication on the last day, the total number of applications expected is as follows:

Date Subject End Participation - Date of Baseline

If the total number of applications exceeds 88 then it will be set to 88.

Compliance will be calculated as a percentage as 100 times the total number of applications taken from the first application until Week 12 divided by the total number of applications expected from first application until Week 12. Subjects who discontinue study medication before Week 12 will be considered to be 0% compliant for the number of days from discontinuing study medication until Week 12.

Compliance will not be calculated for subjects who are lost to follow-up or subjects who have unknown first or last application dates.

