**13.14. On-treatment (Visit 6) – Week 12, Day 85 ( $\pm$  4 days) or End of Treatment or Early Termination**

The following procedures will be conducted at this visit:

- Ask the patient to complete PAPSS, PAPI questionnaire (see [Appendix 2](#) and [Appendix 3](#)). Patient will also complete the PGI-S questionnaire (see [Appendix 4](#)), PGI-C (see [Appendix 5](#)), PGI-TS (see [Appendix 6](#)) and PGI-SE (see [Appendix 7](#)). The PAPSS, PAPI, PGI-S, PGI-C PGI-TS and PGI-SE questionnaires are to be completed prior to any other assessments or procedures as described in [Section 14.5](#).
- Ask the patient to complete Rosacea Quality of Life (RosaQoL) questionnaire (see [Appendix 8](#)).
- Observe and query the patient in a non-directive fashion about any adverse events since the previous study visit.
- Query the patient about any changes in concomitant therapies since the previous study visit and update the Concomitant Therapy eCRF.
- Perform physical examination as described in [Section 13.7](#).

- Perform efficacy evaluations: IGA, inflammatory lesion counts, rosacea erythema assessment, and telangiectasia assessment described in [Sections 14.1 to 14.4](#). The evaluator who performed the Baseline evaluations should perform all subsequent evaluations for a patient. when this is not possible, it is recommended that another delegated evaluator with overlapping experience with the patient may perform the evaluations.
- Perform Cutaneous Safety Assessment and Local Tolerability Assessment as described in [Sections 16.1 to 16.2](#).
- Take standardized photography of face (at selected sites, see separate photographic manual for instructions) as described in [Section 15](#).
- Review the patient's compliance with the study requirements; collect and review the Patient Diary Card.
- Record number of missed doses and report the last date the patient applied the study product.
- Perform a urine pregnancy test for all females of childbearing potential (see [Section 12.2](#)).
- Collect and weigh the study product.
- Complete the End of Study/Study Termination eCRF.
- Discharge the patient from the study.

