#### **19.1.4. Analysis Populations**

Approximately 350 male and female patients at least 18 years of age with moderate or severe papulopustular rosacea with 3 or 4 [moderate to severe] on the IGA scale will be enrolled and randomized in the study with a 2:1 randomization ratio, it is anticipated that:

- 234 patients will be randomized to receive S5G4T-1, Encapsulated Benzoyl Peroxide (E-BPO) Cream, 5%
- 117 patients will be randomized to receive S5G4T-2, Vehicle Cream

The ITT population will consist of all randomized patients who were dispensed study product. The safety population will be comprised of all randomized patients who are presumed to have used the study product at least once and who provide at least one post-baseline safety evaluation.

An intent-to-treat (ITT) analysis will be conducted on all study patients. A per-protocol (PP) analysis will also be conducted. Patients will be eligible for the PP analysis if they complete the 12-week evaluation without noteworthy study protocol violations (i.e., any patient or investigator activity that could have possibly interfered with the therapeutic administration of the treatment or the precise evaluation of treatment efficacy). The PP population will include patients in the ITT population who do not meet any of the following criteria:

- Failed any of the inclusion/exclusion criteria;
- Have taken any interfering concomitant medications;
- Did not attend the Week 12 Visit;
- Missed more than 1 post baseline study visit prior to Week 12
- Have not been compliant with the dosing regimen (i.e., Patients may not miss more than five consecutive days of dosing and must take 80 to 120% of expected doses. The number of expected doses will be determined for each patient based on the length of their participation in the study);
- Out of visit window ( $\pm 4$  days) at the 12-week Visit.

Patients that discontinue from the study due to an adverse event related to study treatment or documented lack of treatment effect will be included in the PP population. Data for these subjects will not be imputed by multiple imputation but rather their data will be imputed with values consistent with their status as treatment failures. Prior to breaking the blind, other additional criteria may be added to the list to accommodate for unforeseen events that occurred during the conduct of the trial that result in noteworthy study protocol violations.

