8.4.4 Per-Protocol (PP) Population

All subjects in the ITT population who complete the Week 12 evaluation without noteworthy study protocol violations (i.e., any patient or investigator activity that could have possibly interfered with the therapeutic administration of the treatment or the precise evaluation of treatment efficacy) will be included in the PP population and analyzed according to the treatment group they received. The PP population will include subjects in the ITT population who do not meet any of the following criteria:

- Failed any of the inclusion/exclusion criteria;
- Have taken any interfering concomitant medications;
- Did not attend the Week 12 Visit;
- Missed more than 1 post-baseline study visit prior to Week 12;
- Have not been compliant with the dosing regimen (i.e., Patients may not miss more than five consecutive days of dosing and must take 80 to 120% of expected applications. The number of expected applications will be determined for each patient based on the length of their participation in the study);
- Out of visit window (± 4 days) at the 12-week Visit.

Subjects that discontinue from the study due to an AE related to study treatment or documented lack of treatment effect will be included in the PP population. Data for these subjects will not be imputed by multiple imputation but rather their data will be imputed with values consistent with their status as treatment failures. See Section 8.1.5 for additional detail. Prior to breaking the blind, other additional criteria may be added to the list to accommodate for unforeseen events that may occur during the conduct of the trial and result in noteworthy study protocol violations.

All efficacy analyses performed on the PP population will be according to the treatment they received.

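### SAP 8.8.1 gives two incompatible denominators for dosing compliance and a numerator that may subtract trailing missed days twice; some early leavers and borderline completers are affected

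*SAP*

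**What the plan says.** **Denominator.** For a patient who applied on the final day, SAP 8.8.1 sets expected applications at "Date Subject End Participation – Date of Baseline +1", capped at 89. Without an application that day it is one fewer, capped at 88. SAP 8.4.4 agrees on the end point: "The number of expected applications will be determined for each patient based on the length of their participation in the study". So does protocol 19.1.4: "The number of expected doses will be determined for each patient based on the length of their participation in the study". The footnote to Listing 16.2.5.2 also refers to length of participation.

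The compliance paragraph later in 8.8.1 divides instead by the applications expected from first application to Week 12. It adds that "Subjects who discontinue study medication before Week 12 will be considered to be 0% compliant for the number of days" from stopping until Week 12. No compliance value is calculated for patients lost to follow-up or with an unknown first or last application date.

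**Flag.** A compliant patient is one who "applied 80% to 120% of the expected number of applications" and "did not miss more than 5 consecutive applications while enrolled in the study". The same two conditions form a PP criterion in 8.4.4.

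**Numerator.** Applications taken are the days from first to last application inclusive, minus the "Number of Days marked as missed applications on the CRF", plus extra applications. At Week 12 or early termination, protocol 13.14 tells sites: "Record number of missed doses and report the last date the patient applied the study product".

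**The concern.** The two denominators end at different points (end of participation, Week 12) and start at different points (Baseline, first application). For a patient who leaves the study early, both cannot be applied, and two programmers following 8.8.1 could produce different flags for the same patient.

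The numerator raises a separate question. Its span stops at the last application, so later days are already left out. Nothing restricts the subtracted missed days to that span, so a day after the last dose that is marked missed would be removed twice.

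At stake are the compliant row of Table 14.3.0.1, Listing 16.2.5.2, the exclusion reasons in Table 14.0.2.1, and the PP status of completers close to 80%.

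**Working it through.** **Inputs.** Week 12 is Day 85 ± 4 days (SAP 6.1 and 8.4.4). The thresholds, caps and formulas are from SAP 8.8.1. Baseline is Day 1.

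**The plan's caps.** The latest in-window visit is Day 85 + 4 = Day 89. Expected applications are 89 − 1 + 1 = 89 with a last-day application and 89 − 1 = 88 without. Both match the SAP. For an on-time visit the counts are 85 and 84.

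**End point of the denominator.** Take a patient who applies daily from Day 1 and leaves the study on Day d. The participation rule gives d/d = 100%. The Week 12 rule gives d/84 or d/85.

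| Leaves on | Participation rule | d/84 | d/85 |
|---|---|---|---|
| Day 43 | 100% | 51.2% | 50.6% |
| Day 57 | 100% | 67.9% | 67.1% |
| Day 67 | 100% | 79.8% | 78.8% |
| Day 68 | 100% | 81.0% | 80.0% |

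The status of such a patient changes up to Day 67. If the Week 12 denominator is taken at its cap, the last day that changes is Day 70 for 88 (70/88 = 79.5%; 71/88 = 80.7%) and Day 71 for 89 (71/89 = 79.8%; 72/89 = 80.9%).

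**Stopping the drug but staying in the study.** With a first dose on Day 1 and a Day 85 visit without a dose, both denominators are 84, so they do not conflict. Stopping on or before Day 78 leaves at least 84 − 78 = 6 consecutive missed applications, which fails the five-day condition under either rule.

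**Start point.** First dose on Day 2, 67 applications, Day 85 visit with no dose that day:
- from Baseline: 67/(85 − 1) = 67/84 = 79.8%, not compliant;
- from first application: 67/(85 − 2) = 67/83 = 80.7%, compliant.

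**Numerator.** First dose on Day 1, 10 scattered misses, last dose on Day 80, Days 81 to 84 missed, Day 85 visit with no dose that day. Expected applications are 84.
- Actually taken: 80 − 10 = 70; 70/84 = 83.3%, compliant.
- As written, if Days 81 to 84 are marked missed: 80 − (10 + 4) = 66; 66/84 = 78.6%, not compliant.

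The four-day gap passes the consecutive-miss condition, so the formula alone removes this patient from PP. In general, a trailing gap of t days subtracts t applications too many. A gap of 6 or more days already fails the consecutive-miss condition. For t = 1 to 5 the loss is 1/84 = 1.2 to 5/84 = 6.0 percentage points. The patients who change status have true counts of 68 to 72 out of 84, that is 81.0% to 85.7%.

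**Exclusion reasons.** Table 14.0.2.1 gives one primary reason in listed order, with non-compliance ahead of an out-of-window visit. A daily user who leaves on Day 50, attends the early-termination visit and meets no earlier-listed reason is out of window under the participation rule (50/50 = 100%). Under the Week 12 rule the same patient is non-compliant (50/84 = 59.5%).

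**The case against.** **Week 12 may mean Week 12 or early termination.** Protocol 13.14 covers both in one visit, and Table 14.0.2.1 labels them together. On that reading the end-point conflict goes. But 8.8.1 does not say so, and the 0% sentence would then be redundant: untreated days within participation are already in the denominator and absent from the numerator. The start-point mismatch would remain.

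**The 0% rule has a defensible purpose.** Without it, a daily user who leaves very early is reported as fully compliant. This stands as a reason to show early stopping somewhere. It does not justify two definitions behind one flag.

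**The double subtraction depends on an unseen CRF convention.** Protocol 13.14 does not say that days after the last dose count as missed. The Listing 16.2.5.2 footnote derives applications from the first and last dates and the applications recorded at deviations, again without settling this. The objection stands, so this half of the point is conditional.

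**Other rules decide most PP cases.** This also stands. Early leavers are mostly excluded for not attending Week 12 or for an out-of-window visit, or are expressly included as treatment failures. Only for the treatment failures might the compliance denominator leave their status unclear.

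**Compliance is not the only exposure measure.** Table 14.3.0.1 also shows days of exposure, applications and missed applications, which limits how far one inconsistent row could mislead.

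**Conclusion.** The denominator conflict is real on the text of 8.8.1, and the participation-based count is the one that the PP definitions and the listing footnote support. It changes the flag of a daily user who leaves the study by about Day 67 (Day 70 or 71 with a Week 12 denominator of 88 or 89). The start-date mismatch can change a patient at the threshold. The numerator defect is conditional on days after the last dose being marked missed. It then affects only patients with a trailing gap of 1 to 5 days and true compliance of about 81% to 86%.

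A reader might infer that nearly every early stopper changes status. That is not so: most who stop the drug but stay on fail the consecutive-miss condition either way, daily users who leave from Day 68 pass under both on-time denominators, and patients lost to follow-up have no value. A reader might also infer a shift of several points in the reported compliance rate, or a difference between arms. The documents give no dropout rate. If 5% to 15% of patients with a compliance value were daily users leaving by Day 67, the compliant share would move by 5 to 15 points, which only restates the assumption. A difference between arms needs the further assumption of unequal dropout.

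The consequences stay within Table 14.3.0.1, Listing 16.2.5.2, the exclusion reasons in Table 14.0.2.1 and a few borderline PP completers. PP is supportive (protocol 19.3), and no ITT analysis changes. The text should still be corrected before unblinding.

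**What to change.** In SAP 8.8.1:

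1. Use one expected count, over the patient's participation and from one stated start date, for both the 80% to 120% flag and the PP criterion in 8.4.4.
2. Remove from that flag the rule that scores days from stopping to Week 12 as 0%. If early stopping should be visible, report applications taken as a percentage of the full 12-week course in a separate, labelled row of Table 14.3.0.1.
3. Subtract only missed days dated between the first and last application. Listing 16.2.5.3 already plans to show dated dosing deviations.

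The cost is SAP wording and derivation code before unblinding. No new data are needed.

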8.8.2 Adverse Events (AEs)

All AEs occurring during the study will be recorded and classified on the basis of MedDRA terminology. Descriptions of AEs will include the date of onset, the date the AE ended, the severity of the AE, the relationship to study product, the action taken regarding study product usage, the action taken to treat the AE, and the outcome. All reported treatment-emergent AEs (TEAEs) will be summarized by the number of patients reporting AEs, system organ class, severity, seriousness, and relationship to study product. TEAEs are those AEs with an onset on or after the date of the first study product application; if the AE is not indicated as prior to first application on the CRF then it will be considered a TEAE.

AEs will be summarized by treatment group and severity. Each patient will be counted only once within a system organ class or a preferred term by using the AEs with the highest severity within each category.

AEs will be summarized by treatment group and relationship to study product. Each patient will be counted only once within a system organ class or a preferred term by using the AEs with the greatest relationship within each category.

If relationship to study drug is reported as definitely, probably, or possible, then this is defined as related. If relationship to study drug is reported as unlikely or not related, then this is defined as unrelated.

Comparisons among treatment groups will be made by tabulating the frequency of patients with one or more AEs (classified into MedDRA terms) during the study. The Fisher's Exact test will be used to compare the proportion of patients in each treatment group who report any AE at a

significance level of 0.05. The specific system organ classes and preferred terms analyzed will be those that are reported by at least one percent of the patients in any treatment group.

All information pertaining to AEs noted during the study will be listed by patient, detailing verbatim given by the investigator, preferred term, system organ class, start date, stop date, severity, actions taken, and drug relatedness. The AE onset will also be shown relative (in number of days) to the day of initial application of the randomized study product.

Serious adverse events (SAEs) will be tabulated by patient within treatment groups.

In addition, a list of patients who discontinued from the study and a list of patients who experienced SAEs will also be provided.

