Clinical Trial Duration	
Screening: -35 to 0 days prior to Baseline
 
Duration of treatment: 12 weeks/84 days
 
Patients have the right to stop the study for any reason at any given time.

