### 17.2. Definitions

An adverse event (AE) is defined as any untoward medical occurrence in a patient administered a medicinal product and which does not necessarily have to have a causal relationship with this treatment. An adverse event can therefore be any unfavorable and unintended sign, symptom, or disease temporally associated with the use of a medicinal product, whether or not considered related to this medicinal product.

A serious adverse event (SAE) is an adverse event that results in any of the following outcomes:

- Death
- Life-threatening event (i.e., the patient was, in the opinion of the investigator, at immediate risk of death from the event as it occurred. It does not include an event that, had it occurred in a more severe form, might have caused death)
- Requires in-patient hospitalization or prolongs hospitalization
- A persistent or significant disability/incapacity or substantial disruption of the ability to conduct normal life functions
- Congenital anomaly/birth defect
- Other adverse events that may be considered serious based upon appropriate medical judgment, may jeopardize the patient and may require medical or surgical intervention to prevent one of the outcomes listed above.

Immediately Reportable Adverse Events (IRAE) is any serious AE or any AE that necessitates discontinuation of study product, including pregnancy.

Unexpected Adverse Event is any adverse drug experience, the specificity or severity of which is not consistent with the current approved product labeling (package insert) for the study product, the Investigator's Brochure, or as described in the clinical protocol and consent materials.

Intensity of Adverse Events are the maximum intensity of an AE during a day should be recorded on the eCRF. If the intensity of an AE changes over a number of days, then separate entries should be made having distinct onset dates for the changes in severity.

- Mild - AEs are usually transient, requiring no special treatment, and do not interfere with patient's daily activities.
- Moderate - AEs typically introduce a low level of inconvenience or concern to the patient and may interfere with daily activities, but are usually ameliorated by simple therapeutic measures.
- Severe - AEs interrupt a patient's usual daily activity and traditionally require systemic drug therapy or other treatment.

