### 17.4. Eliciting and Reporting of Adverse Events

The investigator will periodically assess patients for the occurrence of adverse events. In order to avoid bias in eliciting adverse events, the patient or parent/legally authorized representative should be asked a non-specific question (e.g., "How have you been feeling since your last visit?") to assess whether any AE has been experienced since the last visit. All adverse events (as defined in [Section 17.2](#)), either observed by the Investigator or one of his/her medical collaborators, or reported by the patient spontaneously, or in response to direct questioning, will be reported and documented in the source and the study reporting forms. When reporting an adverse event, the Investigator must assign a severity grade to each event and declare an opinion on the relatedness of the event to the study product or procedure. Serious or unexpected adverse events must be reported to the CRO within 24 hours of when the Investigator first learns of the occurrence of the event.

Adverse events will be documented in the source document and recorded in a timely manner on case report forms. Adverse events that are identified at the last assessment visit (or the Early Termination Visit) must be recorded on the AE eCRF with the status of the AE noted.

Adverse event reporting begins from the signing of informed consent/assent. Study product-related adverse events should be followed until resolved or 30 days after the final study treatment. Regardless the duration of the study, patients that exhibit serious adverse event (SAE), will be followed up until the SAE resolves, based on investigator's medical judgment or are considered to be chronic (stabilized for at least 30 days). All events that are ongoing at this time will be recorded as ongoing on the eCRF.

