
Table 14.3.1.1: Summary of Cutaneous Safety and Tolerability Evaluations
(Safety Population)
(Page 8 of 8)

Burning/Stinging	E-BPO 5% Cream (N=xxx)	Vehicle Cream (N=xxx)
Week 8		
n	xx	xx
0 – None	xx (xx.x%)	xx (xx.x%)
1 – Mild	xx (xx.x%)	xx (xx.x%)
2 – Moderate	xx (xx.x%)	xx (xx.x%)
3 – Severe	xx (xx.x%)	xx (xx.x%)
Week 12		
n	xx	xx
0 – None	xx (xx.x%)	xx (xx.x%)
1 – Mild	xx (xx.x%)	xx (xx.x%)
2 – Moderate	xx (xx.x%)	xx (xx.x%)
3 – Severe	xx (xx.x%)	xx (xx.x%)

Note: No imputation of missing data.

SOURCE: USERNAME\SPONSOR\PROJECT\JOBNAME (DATE,TIME)

Table 14.3.1.2.1: Summary of Treatment-Emergent Adverse Event Characteristics
 (Safety Population)
 (Page 1 of 2)

	E-BPO 5% Cream (N=xxx)	Vehicle Cream (N=xxx)
Subjects Reporting Any Treatment-Emergent Adverse Event	xx (xx.x%)	xx (xx.x%)
Number of Treatment-Emergent Adverse Events	xx	xx
Subjects Reporting Any Serious Treatment-Emergent Adverse Event	xx (xx.x%)	xx (xx.x%)
Number of Serious Treatment-Emergent Adverse Events	xx	xx
Subjects Reporting Treatment-Emergent Adverse Event with Outcome of Fatal	xx (xx.x%)	xx (xx.x%)
Number of Treatment-Emergent Adverse Events with Outcome of Fatal	xx	xx
Subjects Who Discontinued Study Drug Due to a Treatment-Emergent Adverse Event	xx (xx.x%)	xx (xx.x%)
Number of Treatment-Emergent Adverse Events Leading to Discontinuation of Study Drug	xx	xx
Subjects Who Discontinued from the Study Due to a Treatment-Emergent Adverse Event	xx (xx.x%)	xx (xx.x%)
Number of Treatment-Emergent Adverse Events Leading to Discontinuation of Study	xx	xx

Note: Treatment-emergent adverse events are those events that were not indicated as occurring prior to first application.
 Related defined as “Definitely”, “Probably”, or “Possible”. Not Related defined as “Unlikely” or “Not related”.

SOURCE: USERNAME\SPONSOR\PROJECT\JOBNAME (DATE, TIME)

Table 14.3.1.2.1: Summary of Treatment-Emergent Adverse Event Characteristics
(Safety Population)
(Page 2 of 2)

	E-BPO 5% Cream (N=xxx)	Vehicle Cream (N=xxx)
By Maximum Severity		
Severe	xx (xx.x%)	xx (xx.x%)
Moderate	xx (xx.x%)	xx (xx.x%)
Mild	xx (xx.x%)	xx (xx.x%)
By Strongest Relationship to Study Drug		
Related	xx (xx.x%)	xx (xx.x%)
Not Related	xx (xx.x%)	xx (xx.x%)
Maximum Severity within Relationship to Study Drug		
Related		
Severe	xx (xx.x%)	xx (xx.x%)
Moderate	xx (xx.x%)	xx (xx.x%)
Mild	xx (xx.x%)	xx (xx.x%)
Not Related		
Severe	xx (xx.x%)	xx (xx.x%)
Moderate	xx (xx.x%)	xx (xx.x%)
Mild	xx (xx.x%)	xx (xx.x%)

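### AE entries split at each intensity change are never rejoined, so one episode counts as several TEAEs and an improving pre-treatment AE can count as one

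*SAP*

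**What the plan says.** - **Recording.** Protocol 17.2 says that when the intensity of an AE changes over several days, "separate entries should be made having distinct onset dates for the changes in severity". The sentence is not limited to worsening.
- **Classification.** SAP 8.8.2, like Protocol 19.6, sets the rule by onset: "TEAEs are those AEs with an onset on or after the date of the first study product application". The SAP adds a default: "if the AE is not indicated as prior to first application on the CRF then it will be considered a TEAE". The TEAE table footnotes use the flag alone: "Treatment-emergent adverse events are those events that were not indicated as occurring prior to first application". None of these requires worsening from a pre-treatment level.
- **Window before treatment.** Protocol 17.4 states: "Adverse event reporting begins from the signing of informed consent/assent". The synopsis gives "Screening: -35 to 0 days prior to Baseline". The SAP plans a separate listing of pre-treatment AEs (Listing 16.2.7.2.2).
- **Counting.** SAP Table 14.3.1.2.1 has a row "Number of Treatment-Emergent Adverse Events" for each arm, and Table 14.3.1.3.1 has the equivalent row for serious events. Patients are handled differently. In the severity summary, "Each patient will be counted only once within a system organ class or a preferred term by using the AEs with the highest severity", and the relationship summary works the same way. SAP 8.8.2 compares the arms with Fisher's exact test at 0.05, on patients, for classes and terms reported by at least 1% of either arm.

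**The concern.** The unit of recording is a stretch of constant intensity, but the tables present that unit as an event. The two rules are harmless apart and give a wrong result together.

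Two outputs are affected. The event-count rows will depend on how often an AE changed grade as well as on how many AEs occurred. Separately, an event that began before any exposure and then improved can be reported as emerging on treatment. In that case a patient with no new or worse event enters the TEAE incidence and the between-arm tests. At stake is the accuracy of the safety tables. The co-primary efficacy analyses do not use these data.

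**Working it through.** The plan gives no figure on this point, so there is nothing to reproduce. The check applies the written rules to worked cases and then sizes the patient-level effect under stated assumptions.

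**1. Entries per episode.** Under Protocol 17.2, c intensity changes give c + 1 entries. So 1, 2 or 3 changes give 2, 3 or 4 entries.

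**2. On-treatment case.** Mild from Day 5, moderate from Day 8, mild from Day 12: c = 2, so 3 entries. Each has an onset after first application, so the event-count row shows 3 TEAEs for 1 episode. The patient is still counted once within the class or term.

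**3. Pre-treatment case.** Moderate from Day -5, mild from Day 10: 2 entries. The second has onset Day 10. By the onset rule it is a TEAE, and by the flag rule it is a TEAE unless the site marks it as prior. Result: 1 TEAE and 1 patient with a TEAE. Under a rule requiring a first onset or a worsening on treatment, the result is 0 and 0.

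**4. What the once-per-patient rule covers.** It removes the duplication in case 2 from patient counts. It cannot remove case 3, where the continuation entry may be the patient's only TEAE.

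**5. Testing threshold.** With the planned 234 active and 117 vehicle patients (Protocol 12.1), 1% is 2.34 and 1.17 patients. So 3 active or 2 vehicle patients bring a term into the tests.

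**6. Dilution, illustration only.** The TEAE rates and the misclassified share m are assumptions; the documents give neither. If m is the share of patients without a genuine TEAE who gain a false one, equal in both arms, the reported rate is p + (1 − p)m. For p = 0.30 and m = 0.03 this is 0.30 + 0.70 × 0.03 = 0.321. For p = 0.20 it is 0.20 + 0.80 × 0.03 = 0.224. The risk ratio is 0.321 / 0.224 = 1.43. Extra patients are 0.70 × 0.03 × 234 = 4.9 active and 0.80 × 0.03 × 117 = 2.8 vehicle. Fisher p-values use counts rounded to whole patients.

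| Assumed true rates | m | Extra patients, active / vehicle | Risk ratio | Risk difference | Fisher p |
|---|---|---|---|---|---|
| 30% v 20% | 0 | 0 / 0 | 1.50 | 0.100 | 0.041 |
| 30% v 20% | 1% | 1.6 / 0.9 | 1.48 | 0.099 | 0.043 |
| 30% v 20% | 3% | 4.9 / 2.8 | 1.43 | 0.097 | 0.061 |
| 30% v 20% | 5% | 8.2 / 4.7 | 1.40 | 0.095 | 0.084 |
| 20% v 10% | 0 | 0 / 0 | 2.00 | 0.100 | 0.023 |
| 20% v 10% | 1% | 1.9 / 1.1 | 1.91 | 0.099 | 0.026 |
| 20% v 10% | 3% | 5.6 / 3.2 | 1.76 | 0.097 | 0.043 |
| 20% v 10% | 5% | 9.4 / 5.3 | 1.66 | 0.095 | 0.050 |

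At 1% the effect is negligible. At 3% to 5% it could move a borderline comparison. The risk difference barely changes in any row.

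**The case against.** The strongest reply is that the false-TEAE half turns on a CRF that is not in the documents. The working rule is a flag, and Listing 16.2.7.2.4 shows it as a field, so a site could mark a continuation entry as prior. This stands as a limit: such an entry can become a TEAE, but the documents do not show that it must. It does not remove the point, because no instruction tells sites to do this, Protocol 17.2 gives the entry its own later onset, and the default is TEAE.

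Four further points stand:

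- The pre-treatment window may be short. The 35 days is a maximum, and Protocol 13.10 lets Screening and Baseline fall on one day when no washout is needed. The AE must also start after consent, still be present at first application, and then drop a grade rather than simply resolve.
- A reader might infer that application-site irritation is inflated most. The documents do not support this. Protocol 16.1 and 16.2 keep dryness, scaling, itching and burning/stinging out of AE recording unless they lead to a treatment interruption, withdrawal or a new medication. They are graded and tabulated separately.
- A reader might infer that duplicate entries distort the Fisher tests. They cannot, because those tests count patients. Only the pre-treatment case reaches them.
- The listings give dates and severity for every entry, so a split episode can be traced by hand.

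It could also be said that a footnote calling the counts entry counts would be enough. That would make the unit clear, but it would leave the treatment-emergent status of continuation entries to each site.

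**Conclusion.** The point holds and is minor. Followed literally, the plan reports one on-treatment episode with c intensity changes as c + 1 TEAEs in the event-count rows. It also lets an AE from the consent-to-first-application period that eases later count as a TEAE, unless the site flags the continuation entry as prior. Patient counts per class or term are protected from the first effect but not the second.

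The first effect follows directly from the text, but only for episodes that change grade. The size of the second is unknown. It is tempting to attach a number of affected patients, but no document figure anchors one, and the shares in the table above are assumptions. Any such patient who also has a genuine TEAE is already in the any-TEAE row. Randomisation should make the misclassification similar in both arms, so the expected result is inflated descriptive event counts and some dilution in TEAE rates, with no systematic bias towards either arm.

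**What to change.** Amend SAP 8.8.2 before unblinding:

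1. Link entries that continue the same event in a patient: same preferred term, with the next start on the day of the previous stop or one day later. Send unclear cases and incomplete dates to blinded review, so that distinct events are not merged. The review is needed because SAP 8.1.5 imputes medication dates but not other safety data.
2. In the event-count rows, count each linked episode once, at its maximum severity and strongest relationship. Treat it as serious if any entry is serious, carry over any discontinuation or action recorded on any entry, and take the outcome from the last entry.
3. Classify an episode as treatment-emergent only if its first onset is on or after first application, or if its intensity from then on exceeds its highest intensity before. A pre-treatment AE that worsens on treatment is still captured.
4. Keep all entries in the listings, and footnote that event counts in the tables are episodes.

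Cost: a short derivation and a blinded review step. The dates, terms, severity, relationship, action and outcome are already collected, so no new data are needed. The drawback is that event counts in the tables will differ from the number of entries listed, which the footnote must explain.
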